who are infertile will not be asked to take pregnancy test per PI discretion. The patient will be instructed to begin the secondary treatment (placebo or Ivabradine) for one month.

-At Visit 6, two-weeks into this treatment, the patient will return to ACTRI for drug titration. Orthostatic heart rate will be monitored. If the patient fulfills criteria (see **Ivabradine Dosing** below), they will either increase, decrease, stop, or not change their Ivabradine dose.

-At Visit 7, one month after starting the secondary treatment, the patient will return for orthostatic heart rate monitoring, NE bloodwork, and QOL questionnaires.

Blood samples will be saved and securely stored with the PI for future research analysis and purposes.

**Randomization.** Randomization refers to the order in which patients receive placebo or Ivabradine. If a patient receives Ivabradine first for one month, then he/she will be switched over to placebo for one month. If a patient receives placebo first for one month, then he/she will be switched over to Ivabradine for one month. There will be a one-week washout period prior to the cross-over. There will be 10 patients in each group.

**Ivabradine Dosing.** Ivabradine dose will initiate at 5mg twice daily (bid) and be increased to 7.5mg twice daily (bid) after 2 weeks if the heart rate is greater than 70 beats/min. If the heart rate is less than 70 beats/min there will no increase in dose. If the heart rate is less than 50 beats/min, or if the patient has symptoms of dizziness or lightheadedness, then Ivabradine will be stopped.

If patients have side effects and feel that cannot continue with Ivabradine we will decrease the dose from 7.5mg bid to 5mg bid (or if they are on 5mg bid to 2.5mg bid). After this dose reduction if the patient is still unable to tolerate Ivabradine, we will stop Ivabradine and withdraw patient from the study. If a patient is unable to tolerate Ivabradine (particularly prior to crossover period), he/she will be withdrawn. The starting dose and titration model is the same for the crossover treatment period as the initial month.

In our clinical experience using Ivabradine in patients with inappropriate sinus tachycardia (which are very similar to POTS patients in age and co-morbidities) we have not seen significant side effects that have caused patients to stop the drug. Refer to the uploaded Ivabradine Drug Information document for more details.

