**Statistical Analysis.** Continuous variables including mean heart rate, maximum heart rate, and quality of life scores will be summarized using descriptive statistics, including the number of observation (n) mean, standard deviation (SD), standard error (SE), median, the 1st (Q1) and 3rd (Q3) quartiles, minimum, and maximum values. The change in heart rate at one month from baseline will be compared by T-tests based on treatment status with placebo versus Ivabradine. Categorical variables will be compared by McNemar's test based on treatment status with placebo versus Ivabradine.

The study design will be adaptive and data analysis will be done in batches. The PI and others involved in data analysis will be blinded to who is the Ivabradine group and who is in the placebo group.

**Power Analysis.** Assuming a decrease in average heart rate of 10 beats/min is clinically significant (e.g. Decrease from 100 to 90; magnitude of effect 10%) with power 0.8 and standard deviation in heart rate is 7.5 beats/min, the estimated sample size is 18 patients. We will enroll 10 patients in each group to account for the 10% drop-out rate and to ensure the study is adequately powered. For sample size calculation, two-sided alpha level = 0.05 and two sample t-test are used.

**Drop-outs.** If any patient decides to withdraw from the study due to the intolerance of side-effects, we will try to obtain a tilt table test, orthostatic heart rate, QOL questionnaire, and blood tests at the time of drop-out.

**Documentation.** All patient related documentation will be stored at UCSD for future analysis as funding becomes available. To minimize the potential loss of confidentiality, patients will be assigned a unique number as their subject identifier code. The unique subject code will be used to label all study documents. The key that relates the code numbers to the individuals will be kept in a locked cabinet in the PI's office at the ACTRI.

All procedures mentioned above are research procedures and are not part of standard care.

Results may be used for diagnosis, treatment, and prevention of disease in patients.

**Incidental findings that result from the conduct of this study that require medical intervention for the subject will be noted by the PI or her project's medical research staff. They will refer the subject to his primary care physician. If the subject does not have a primary care physician one will be appointed for him or her.**

---

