  - b. In the event of an AE that occurs during the appointment, the facility is equipped with trained medical staff (physicians and nurses) who can respond quickly. Should an event occur, [name] and the nurses will be nearby to administer immediate medical care and send the patient to the nearest hospital. If the AE occurs after the appointment, the patient will be referred for prompt medical attention. The patient will be withdrawn from the study. [name] will monitor the patient until the problem has been resolved or has stabilized.
3. Orthostatic heart rate monitoring:

- a. Prior to enrollment, the patient will be informed about the risks of orthostatic heart rate monitoring. The physician will comfort the patient to reduce anxiety/fear in order to minimize the probability of a vasovagal response. [name] will continuously monitor and oversee the procedure by checking vital signs. The patient may contact [name] for further questions/concerns.
  - b. In the event of an AE that occurs during the appointment, the facility is equipped with trained medical staff (physicians and nurses) who can respond quickly. Should an event occur, [name] and the nurses will be nearby to administer immediate medical care and send the patient to the nearest hospital. If the AE occurs after the appointment, the patient will be referred for prompt medical attention. The patient will be withdrawn from the study. [name] will monitor the patient until the problem has been resolved or has stabilized.
4. Consuming Ivabradine
- a. [name], a cardiologist, will give the patients specific instructions on the amount of ivabradine capsules they would need to consume each day. A research person will follow up with the patient the next day and once a week for the next 90 days to assess the patient's condition. The patient's conditions will be reported back to the PI. If the patients have reasons to believe that Ivabradine is causing any discomfort, consumption of the capsule will be stopped.

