  - b. In the event of an AE that occurs during the appointment, the facility is equipped with trained medical staff (physicians and nurses) who can respond quickly. Should an event occur, [name] and the nurses will be nearby to administer immediate medical care and send the patient to the nearest hospital. If the AE occurs after the appointment, the patient will be referred for prompt medical attention. The patient will be withdrawn from the study. [name] will monitor the patient until the problem has been resolved or has stabilized.
5. Washout Period
- a. [name] will monitor the patients closely during this washout period. [name] will remove patients from the study if it is in their best medical interest. A research person will follow up with the patient once a week during this period to assess the patient's condition. The patient's conditions will be reported back to the PI.
  - b. If an AE occurs, the patient will be referred for prompt medical attention. The patient will be withdrawn from the study. [name] will monitor the patient until the problem has been resolved or has stabilized.

In the event that a patient either withdraws from the study or the investigator decides to discontinue a patient due to SAE, the patient will have appropriate follow-up medical monitoring. Monitoring will continue until the problem requiring hospitalization has resolved or stabilized with no further change expected, is clearly unrelated to study medication, or results in death.

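### McNemar's test, the only method given for categorical variables, cannot use a patient whose first-period or washout adverse event ends participation, so it is unsuited to adverse events, stopping and withdrawal

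*Combined protocol and SAP*

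**What the plan says.** All references are to the combined protocol and SAP.

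- **Section 9, Statistical Analysis.** The whole rule for categorical data is "Categorical variables will be compared by McNemar's test based on treatment status with placebo versus Ivabradine". No categorical variable is named. There is no analysis set and no rule for a patient with one period only. The variables named in that paragraph, heart rate and quality-of-life scores, are continuous.
- **Section 9, Randomization.** The pair is the two periods of one patient: "If a patient receives Ivabradine first for one month, then he/she will be switched over to placebo for one month", or the reverse order. "There will be 10 patients in each group".
- **Section 9, Ivabradine Dosing.** Side effects lead first to a lower dose. Then: "After this dose reduction if the patient is still unable to tolerate Ivabradine, we will stop Ivabradine and withdraw patient from the study". Also: "If a patient is unable to tolerate Ivabradine (particularly prior to crossover period), he/she will be withdrawn".
- **Section 15, AE Management, item 4b (taking ivabradine).** "If the AE occurs after the appointment, the patient will be referred for prompt medical attention. The patient will be withdrawn from the study". The items on blood draw, tilt test and orthostatic monitoring read the same way. Item 5b, on the washout, says: "If an AE occurs, the patient will be referred for prompt medical attention. The patient will be withdrawn from the study". None of these clauses states a severity threshold.
- **Section 9, Drop-outs.** "If any patient decides to withdraw from the study due to the intolerance of side-effects, we will try to obtain a tilt table test", together with orthostatic heart rate, questionnaire and blood tests. This is one assessment at exit.
- **Sections 10 and 11.** Expected drop-out is 10%, so 20 patients give 18 for analysis.

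**The concern.** McNemar's test compares two discordant cells: event on ivabradine only, and event on placebo only. To be placed in any cell, a patient must have been observed on both treatments. Here the event being counted can itself remove the second observation. An ivabradine-first patient who has an adverse event and is withdrawn never has a placebo period and is left out. The same holds for a placebo-first patient with an event on placebo, and for anyone withdrawn in the washout. The exit assessment does not supply the missing period.

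Withdrawal as an outcome is worse placed. A withdrawal in period 1 has no period 2 by definition, so only period-2 withdrawals could ever be counted.

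Section 6 describes the aim as an effective and safe treatment, and no other treatment comparison of adverse events is planned. A paired test restricted to patients who got through period 1 would describe the tolerant patients and leave out some of the events that matter most.

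**Working it through.** **The plan's own figures.** The documents give no figure for McNemar's test or for adverse events. The stated sample size concerns heart rate. By the normal approximation, 2 × (1.960 + 0.842)² × 7.5² / 10² = 8.8, so 9 per group and 18 in total; 18 / 0.9 = 20. It reproduces but does not bear on this point. The figure that does is the drop-out: 10% of 20 is 2 patients.

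**Inputs.** There are 10 patients per sequence (Randomization). Event risks are p on ivabradine and q on placebo; *w* is the share of events that end participation. The documents give none of these three, so all are assumptions. I also assume independence between periods, no period effect, no drop-out for other reasons, and the exact form of McNemar's test.

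**Formulas, with the same *w* on both treatments.**
- Ivabradine events: 10p + 10(1 − wq)p, of which 10pw cannot enter the test.
- Placebo events: 10q + 10(1 − wp)q, of which 10qw cannot enter.
- Withdrawn: 10pw + 10qw + 10(1 − wp)qw + 10(1 − wq)pw.
- Expected discordant pairs: ivabradine only b = 20p(1 − q)(1 − w/2); placebo only c = 20q(1 − p)(1 − w/2).
- Rejection rate: within the ivabradine-first sequence a patient falls in b with probability p(1 − w)(1 − q) and in c with probability (1 − p)q; within placebo-first, p(1 − q) and q(1 − w)(1 − p). The joint probabilities are summed over all (b, c) with exact two-sided p ≤ 0.05.

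**Results at p = 30%, q = 10%.**

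| | w = 0 | w = 0.25 | w = 1 |
|---|---|---|---|
| Withdrawn, of 20 | 0 | 1.96 (9.8%) | 7.4 (37%) |
| Ivabradine events: expected / lost | 6.0 / 0 | 5.93 / 0.75 (13%) | 5.7 / 3.0 (53%) |
| Placebo events: expected / lost | 2.0 / 0 | 1.93 / 0.25 (13%) | 1.7 / 1.0 (59%) |
| b : c | 5.4 : 1.4 | 4.7 : 1.2 | 2.7 : 0.7 |
| Rejection rate | 19% | 14% | 1.4% |

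The middle column is the one consistent with the planned drop-out.

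**Lower rates, p = 10%, q = 5%.** With w = 1, withdrawals are 1 + 0.5 + 0.45 + 0.95 = 2.9 of 20 (14.5%). The loss is 1.0 of 1.95 ivabradine events (51%) and 0.5 of 0.95 placebo events (53%). To match 2 withdrawals, 3w − 0.1w² = 2 gives w = 0.68. The loss is then 0.68 of 1.97 ivabradine events and 0.34 of 0.97 placebo events, about 35% of each. The percentage is higher than at 30/10%, but in both cases about one patient is lost, because roughly half of two withdrawals fall in period 1.

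**Direction.** With equal *w*, the factor (1 − w/2) cancels and b/c is unchanged: 5.4/1.4 = 2.7/0.7 = 3.9. If only ivabradine events end participation, b shrinks and c does not. At 30/10% with w = 1, b : c = 2.7 : 1.4, a ratio of 1.9. If such withdrawals make up the planned 2 patients, 6w = 2 gives w = 1/3, b = 5.4 × (1 − 1/6) = 4.5, and b : c = 4.5 : 1.4, a ratio of 3.2.

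**A concrete case.** Exact McNemar needs at least six discordant pairs, all one way, for p < 0.05 (6:0 gives 0.031; 5:0 gives 0.0625). Six ivabradine-only events, three per sequence, become 3:0 (p = 0.25) if the three period-1 cases are withdrawn.

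**The case against.** The strongest reply is that the plan never says adverse events will be tested by McNemar. The endpoints in section 6 are heart rate and quality of life, and the study is described as proof of concept. Section 15 has adverse events graded, attributed and reviewed individually and in aggregate. This stands in part. A reader might infer that first-period events disappear from the trial; they do not, since they are recorded and reviewed. What is missing is a treatment comparison that can include them. If the sponsor never meant McNemar for adverse events, the plan has no method for them and needs the same wording.

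A reader might also infer that about half of all events vanish. That requires withdrawal at every event. Section 9 puts dose reduction before withdrawal, whereas section 15 withdraws after an adverse event without qualification. The documents conflict, and the larger figure rests on one side of the conflict. At 30/10% it also implies 37% withdrawn, against the 10% expected.

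A third tempting reading is that the plan is shown to favour ivabradine. The intolerance rule is worded for ivabradine only, which points that way. But the trial is double-blind, and if the rule is applied alike to both treatments the discordant ratio does not move. Bias is conditional.

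Finally, low power is mainly a matter of size. With every patient completing, the test rejects only 19% of the time at 30/10% and 0.4% at 10/5%. A period-1 Fisher test of 10 against 10 rejects 5.7% and 0.1%. This stands: no choice of test makes this trial able to detect a moderate excess. The case for change is that all exposed patients should be counted and shown.

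**Conclusion.** The point holds in a limited form. Under the only categorical method stated, a patient whose period-1 or washout event or intolerance ends participation cannot enter the comparison, and withdrawal cannot be paired. Nothing else in the plan repairs this.

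The size is uncertain because the event rates and the share of events ending participation are assumptions. At 30/10%, the loss runs from about 13% of events, if withdrawals match the planned drop-out, to 53% of ivabradine and 59% of placebo events if every event causes withdrawal. At the planned drop-out it amounts to about one patient in 20. The harm is lost events and power if withdrawal is even-handed, and a comparison tilted towards ivabradine if it follows mainly ivabradine intolerance. The defect is worth correcting before analysis because the correction is cheap and the omitted patients are selected by the outcome itself. It does not touch the heart-rate endpoint calculation.

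**What to change.** 1. Name the categorical variables. Keep McNemar's test for those observed in both periods, and do not use it for adverse events, stopping or withdrawal.
2. Tabulate adverse events, stopping and withdrawal by treatment at onset, among all patients who took at least one dose of that treatment, including those later withdrawn, with exact 95% intervals. State in advance how washout events are assigned.
3. Show withdrawals by treatment and period, with the reason. Period-2 denominators contain only patients who got through period 1, so the split by period is needed to read the table.
4. Optionally add a period-1 exact comparison as supportive. It excludes no one withdrawn in period 1, but it discards period 2 and has very low power at 10 against 10; the plan should say so.
5. Reconcile section 9, Ivabradine Dosing (dose reduction before withdrawal) with section 15, AE Management (withdrawal after an adverse event), so that it is clear which events end participation. Which rule applies is a clinical decision for the investigators.

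The statistical changes cost analysis-plan wording and one table. No new data, visits or patients are needed. Item 5 needs a wording clarification in the protocol.

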## **9. RESEARCH DESIGN AND METHODS**

**Overall Study Design.** The clinical trial will be registered under [www.clinicaltrials.gov](http://www.clinicaltrials.gov). Subjects between the ages of 18-65 who have a POTS diagnosis will be enrolled. Specifically, we will enroll patients who have hyperadrenergic POTS as confirmed by norepinephrine (NE) levels > 600 pg/ml. This is a 3-month study with a randomized double-blind placebo controlled cross over design. Subjects will be randomized into one of two groups (Ivabradine or placebo for one-month) then crossed over after a one-week washout period to the other group for one-month. Refer to Figure 1 below for details.

[figure not shown]

Figure 1. Randomized double-blind placebo-parallel group crossover trial with Ivabradine for patients with POTS.

**Study Visits.** There will be seven visits at the ACTRI and UCSD Cardiology clinics.

-Visit 1 is the pre-screening visit during which norepinephrine (NE) blood results will be obtained to confirm hyperadrenergic POTS diagnosis (NE> 600pg/ml). Orthostatic heart rate will be monitored. A urine pregnancy test will also be administered at this time. Post-menopausal women and women who are infertile will not be asked to take pregnancy test per PI discretion.

-At Visit 2, baseline lab work will be obtained to assess cardiometabolic health (CBC, CMP, TSH, T4, BNP). A tilt table test will be performed to determine baseline heart rate and QOL questionnaire (ShortForm36, SF36) will be completed. Orthostatic heart rate will be monitored. At this point, the patient will be randomized into the Ivabradine or placebo group for one month.

-At Visit 3, two-weeks into treatment, the patient will return to ACTRI for drug titration. Orthostatic heart rate will be monitored. If the patient fulfills criteria (see **Ivabradine Dosing** below), they will either increase, decrease, stop, or not change their Ivabradine dose.

-At Visit 4, one month after starting the current treatment, orthostatic heart rate monitoring, NE bloodwork, and QOL questionnaires will be completed. There will be a one-week wash-out period before the patient crosses over to the other group for one month.

-At Visit 5, the patient will return for orthostatic heart rate monitoring, NE bloodwork, and QOL questionnaires. A urine pregnancy test will be administered at this time. Post-menopausal women and women

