### Monitoring procedures

[name] assures that informed consent is obtained prior to performing any research procedures, that all subjects meet eligibility criteria, and that the study is conducted according to the IRB-approved research plan. Study data are accessible at all times for the PI to review. The PI reviews study conduct such as accrual, drop-outs, protocol deviations on a monthly basis. The PI reviews AEs individually real-time and in aggregate on a weekly basis. The PI reviews serious adverse events (SAEs) in real-time. The PI ensures all protocol deviations, AEs, and SAEs are reported to the IRB according to the applicable regulatory requirements.

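### The declared blind is poorly protected: heart rate reveals treatment, the titration rules name only ivabradine, and the self-reported SF-36 is listed after heart-rate monitoring

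*Combined protocol and SAP*

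**What the plan says.** Section 9, Overall Study Design: "This is a 3-month study with a randomized double-blind placebo controlled cross over design". Statistical Analysis in the same section adds: "The PI and others involved in data analysis will be blinded to who is the Ivabradine group", and to the placebo group likewise. The PI is thus counted among those who analyse the data.

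Orthostatic heart rate is listed at each of the seven visits. Visits 3 and 6 are for titration, which turns on heart rate and tolerance. If criteria are met, "they will either increase, decrease, stop, or not change their Ivabradine dose". The Ivabradine Dosing paragraph words every increase, hold, reduction, stop and withdrawal step for ivabradine. In Section 15, AE Management, a cardiologist gives patients "specific instructions on the amount of ivabradine capsules they would need to consume each day".

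Under Monitoring procedures in the Data Safety Monitoring Plan, "Study data are accessible at all times for the PI to review". The PI also reviews each adverse event in real time. Bradycardia and phosphenes are on the list of events expected with ivabradine.

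The SF-36 is the quality-of-life instrument, and quality of life is the secondary endpoint. At Visit 4, "orthostatic heart rate monitoring, NE bloodwork, and QOL questionnaires will be completed". At Visits 5 and 7, "the patient will return for orthostatic heart rate monitoring, NE bloodwork, and QOL questionnaires". At Visit 2 the SF-36 is listed after the tilt test and before orthostatic monitoring.

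The supplied text does not describe how placebo is handled at titration, who titrates, whether readings are withheld from patients, or any check of the blind.

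**The concern.** A declaration of blinding does not keep a blind when the treatment acts directly on a quantity that is measured at every visit and then acted on. Here there are three sources of information about the arm: the heart-rate readings, the side effects expected with the drug, and the dose changes themselves if only ivabradine patients have them. In a crossover, a correct guess for one period settles the other.

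The hypothesis covers functional status as well as tachycardia, and the SF-36 is the patient's own account of it. A patient who has worked out the treatment, or takes a cue from staff who have, may score according to expectation. The background section justifies the trial by the lack of randomised, placebo-controlled evidence, and an SF-36 difference driven by expectation would not supply it. This cannot be repaired once the questionnaires are in.

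**Working it through.** **Inputs.** From Section 9, Power Analysis: difference 10 beats/min, SD 7.5 beats/min, power 0.80, two-sided alpha 0.05, two-sample t-test, stated sample size 18. Not in the documents: the within-patient correlation r (taken as 0, 0.5 and 0.7) and a smaller true effect of 5 beats/min (taken as a sensitivity case).

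**1. The plan's own figure.** n per group = 2 × [7.5 × (1.960 + 0.842) / 10]² = 8.83, rounded up to 9, so 18 in total. The stated 18 reproduces by the normal approximation. The point changes neither sample size nor power; the check only confirms that 10 and 7.5 are the planning values.

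**2. The passages side by side.** The blinding statement covers the PI and the analysts. The titration text sends every patient to Visits 3 and 6 but describes changes to the ivabradine dose only. Either dose changes happen only on ivabradine, and then a change reveals the arm, or the same steps are run with placebo capsules in both periods, and then the text does not say so. The two sections need reconciling.

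**3. What one reading tells.** Suppose an observer calls a reading below the midpoint of the two treatment means ivabradine, and one above it placebo. The chance of being right is Φ(difference / (2 × SD)).
- 10 beats/min: Φ(10/15) = Φ(0.667) = 0.748
- 5 beats/min: Φ(5/15) = Φ(0.333) = 0.631

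**4. What both periods tell.** An observer who calls the period with the lower reading ivabradine is right with probability Φ(difference / (SD × √(2(1 − r)))).

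| r (assumed) | 10 beats/min | 5 beats/min |
|---|---|---|
| 0 | Φ(0.943) = 0.827 | Φ(0.471) = 0.681 |
| 0.5 | Φ(1.333) = 0.909 | Φ(0.667) = 0.748 |
| 0.7 | Φ(1.721) = 0.957 | Φ(0.861) = 0.805 |

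If 7.5 were instead the SD of the within-patient difference, the 10 beats/min result would be Φ(10/7.5) = 0.909.

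**5. Scope of these figures.** They apply to someone who holds the readings, and an intact blind would give 0.5. Step 3 also requires a rough idea of the two means. Step 4 ignores period and carryover effects and cannot apply to the SF-36 at Visit 4, when only one period has been seen. Adverse events and dose changes are left out. None of the figures measures bias in the SF-36.

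**The case against.** The strongest reply is that the documents do not say what the alarming version of this point needs.

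- **The PI's role.** A reader might infer that the PI personally takes each reading and sets each dose. The visit descriptions are in the passive and name no titrator, and the names in AE Management have been removed. Only access to study data and review of adverse events are firmly attributed to the PI.
- **Knowing the arm.** A reader might infer that whoever titrates must know the treatment. That does not follow. The triggers are heart rate, symptoms and tolerance, all observable without the code, and the starting dose and titration model are said to be the same in both periods. With matching capsules the rules can be run blind.
- **Access to the code.** Access to study data is not access to the allocation. The key in the PI's office links subject codes to individuals and is not said to be the treatment list.
- **Order and disclosure.** Order of listing is not order of administration, and no section says that patients are told their heart rate.
- **Importance.** The primary endpoint is measured. The SF-36 is secondary, and the t-test sentence names heart rate only. Some functional unblinding is unavoidable with a drug of this kind, and real-time adverse-event review is ordinary safety oversight in a trial without a monitoring board.
- **Material not supplied.** The consent form and drug documents are held elsewhere and may describe the placebo.

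All of this stands, and it narrows the point. It does not answer the inconsistency between arm-specific dosing text and a blinding statement, or the lack of any provision separating a subjective outcome from an informative measurement.

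**Conclusion.** The point holds in a limited form: the blind is declared but weakly protected. Taken literally, the dosing text would reveal the arm through dose changes. If titration is in fact run blind, heart rate still carries information: about 75% correct from one reading and 83–96% from two periods at the planned 10 beats/min, falling to 63% and 68–81% at 5 beats/min. These figures rest on normality, a common SD of 7.5, r between 0 and 0.7, and an observer who sees the readings.

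The main exposure is the SF-36. For heart rate, reporting bias is a smaller worry, although knowing the treatment could still influence titration and withdrawal decisions. The documents do not establish that the blind will fail, that the PI is unblinded, or that patients see their readings before completing the questionnaire. The changes should be made because they cost little and protect the secondary endpoint.

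**What to change.** 1. At Visits 2, 4, 5 and 7, have the SF-36 completed before any heart-rate or tilt testing and before symptoms are discussed. Do not tell patients their readings unless safety requires it.
2. Reconcile the titration text (Section 9, Visits 3 and 6 and Ivabradine Dosing) and the capsule instructions (Section 15, AE Management) with the blinding statement. Word them for study drug (ivabradine or matching placebo), so that the existing steps are run identically and blind in both periods. No dose, threshold or stopping criterion needs to change for this purpose.
3. Keep the Visit 3 and 6 titration readings and the adverse-event narratives from whoever analyses the SF-36 until database lock. The plan analyses data in batches, so the restriction must cover each batch. The PI needs adverse-event information for safety, so someone else should handle the SF-36 before lock.
4. Optionally, record the patient's and the PI's treatment guess at Visits 4 and 7 and report the guesses descriptively. Do not analyse the SF-36 by correctness of guess. That conditions on a post-randomisation variable that may itself reflect benefit, and at 83–96% correct only about 1 to 3 of 18 patients would be wrong (18 × 0.043 = 0.8; 18 × 0.173 = 3.1).

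Cost: re-ordering existing assessments, wording changes, a rule on file access and, if item 4 is adopted, a short question to each party. No extra visits are needed. The small downside is that patients are not routinely told their heart rate on the day.
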